4. STUDY DESIGN

4.1. Investigational plan

4.1.1. Study plan

The present CL2-95014-003 study is a multicentre, non-randomized roll-over study of lyophilized Pegasparagase (Oncaspar®, S95014) formulation in the treatment of pediatric patients with ALL who completed the CL2-95014-002 study during the induction phase.

Written informed consent and assent (when appropriate) will be obtained from each patient and/or his/her parent(s)/legal representative during the inclusion visit, corresponding to the withdrawal visit of the initial CL2-95014-002 study.

[figure not shown]
Lyophilized S95014 will be administered every two weeks during the consolidation phase at the dose of 1000, 2000 or 2500 U/m², as per investigator's judgment. Patients will be administered 9 infusions of lyophilized S95014, at week 7, 9, 11, 15, 17, 19, 23, 25 and 27 (3 phases S1, S2 and S3). Patients will receive other backbone chemotherapy agents as per ALL-MB 2015 protocol.

The study duration will be approximately 7 months, including the treatment period consisting of the consolidation phase and the follow-up period. After completing the consolidation phase, patient will be discontinued from the study and will be treated as per investigator's judgment.

For more details about the statistical analyses please refer to the [section 10](#).

The study plan is shown in [Figure \(4.1.1\) 1](#).

Figure (4.1.1) 1 – Study plan

The study will be divided into the following periods for each participant:

- **Inclusion visit:** to obtain informed consent and check the inclusion/non-inclusion criteria. The inclusion visit of CL2-95014-003 study will correspond to the withdrawal visit of the initial CL2-95014-002 study.
- **Treatment period:** As per ALL-MB 2015 protocol, treatment period will start at Day 1 of the consolidation phase. Patients will be on treatment until the end of the consolidation phase, unless they meet a discontinuation criterion as described in [section 5.6.1](#).
- **Withdrawal visit:** up to 30 days after the last dose of S95014 during the consolidation phase. Patient will continue receiving backbone chemotherapeutic regimen as per ALL-MB 2015 protocol, according to physician's judgment.
- **Follow-up visit:** a contact or telephone call will be done approximately 30 days after the last S95014 infusion, except in case of consent withdrawal. Follow-up of adverse events and the patient's survival will be recorded.

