6. TREATMENT OF PARTICIPANTS

6.1. IMP and NIMPs administered

6.1.1. IMP

S95014 lyophilizate is considered as the study IMP.

S95014 dosage is calculated according to body surface area (BSA). The BSA will be calculated by the investigator based on the height and weight measured on the day of S95014 infusion (all BSA calculations are rounded to 2 decimal places). Height and weight measured within 3 days before the date of S95014 infusion will be acceptable.

$$\text{BSA (m}^2\text{)} = \sqrt{(\text{Height [cm]} \times \text{Weight [kg]})/3600}$$

Study sites are required to use only calibrated and certified scales throughout the study.

Lyophilized S95014 will be administered IV, over 1 to 2 hours, every two weeks during the consolidation phase at the dose of 1000, 2000 or 2500 U/m², as per investigator's judgment. Patients will be administered 9 infusions of lyophilized S95014, at week 7, 9, 11, 15, 17, 19, 23, 25 and 27 (3 phases S1, S2 and S3). Patients will receive other backbone chemotherapy agents as per ALL-MB 2015 protocol.

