6.3. Previous and concomitant treatments

If a patient receives any drug other than S95014 and backbone therapies used in the frame of ALL-MB 2015 during the period from the day of informed consent to the withdrawal day, the following information will be entered in eCRF:

- Name of drug or therapy
- Start date and end date of treatment
- Route of administration
- Indication

The following treatments are to be used with caution during the whole treatment period:

- Live vaccines
- Coumarin/warfarin and heparin, dipyridamole, acetylsalicylic acid or non-steroidal anti-inflammatory medicines (e.g. ibuprofen, naproxen).
- Prednisone, methotrexate, vincristine, cytarabine (see ALL-MB 2015 protocol for further details)

For further information about the drug-drug interactions, please refer to the last version of the [Investigator's Brochure](#).

The patient and his/her parent(s)/legal representative must be told to notify the investigational site about any new medications he/she takes after having signed the ICF of the study. All medications (other than study drugs) and significant non-drug therapies (including blood transfusion) administered during the study must be listed on the eCRF.

For a given patient, previous treatments and concomitant treatments already reported in the initial CL2-95014-002 study and not ongoing at the time of inclusion, will not be reported in the eCRF.

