8.1. Specification of safety parameters

Safety measurements performed during the study are indicated in [Table \(4.1.2\) 1](#).

Safety assessment of lyophilized S95014 will include:

- adverse events (AEs) assessments
- physical examinations, performance status ECOG (see [Appendix 2](#))
- laboratory assessments including haematology, blood biochemistry, coagulation parameters, urinalysis, hepatitis serology
- vital signs measurements

Adverse events will be collected regardless of grade or IMP relationship and will be graded according to current National Cancer Institute (NCI) CTCAE criteria 5.0

Any significant abnormality detected during safety assessments from the patient ICF signature until the withdrawal visit must be reported on the adequate eCRF page by the investigator at each visit (AE, medical history or sign & symptoms).

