Biochemistry	Albumin, Alkaline Phosphatase (ALP), ALT, AST, Ammonia, Bicarbonates, Gamma-glutamyl-transferase (GGT), Lactate dehydrogenase (LDH), Calcium, Phosphorus, Sodium, Potassium, Creatinine, Total Bilirubin, Total Cholesterol, LDL, HDL, Triglycerides, BUN or Urea, Uric Acid, Amylase, Lipase, Glucose
Urinary analysis	Macroscopic Panel (Dipstick) (Blood, Glucose, Ketones, Protein) If the dipstick test is at least 2+ on one or more parameter(s), quantitative urinary biochemistry tests will be performed on the abnormal parameter(s)
Blood coagulation	Prothrombin time - International Normalized Ratio (INR), fibrinogen, protein S activity, antithrombin activity, activated Partial Thromboplastin Time (aPTT), D-dimer, FDP
Hepatitis serology	HbsAg, HbsAb, HbcAb, if HbsAg or HbcAb positive check viral load (HBV-DNA) at baseline, HCV RNA-PCR, HEV RNA-PCR
Pregnancy Test	Pregnancy testing is mandatory at inclusion (serum), before each phase of the consolidation (i.e. S1, S2, S3) and at withdrawal visit (serum) for WOCBP

All samplings for biochemistry should be taken in fasting conditions.

Abnormal laboratory values or test/exams results (i.e. blood pressure recording) will constitute an AE if they are:

- associated with signs and symptoms, or
- deemed clinically significant in the investigator's opinion, or
- if they require curative therapies, or
- associated with delay of study medication, or
- associated with study discontinuation

Triplet ECG will be assessed at inclusion and at the withdrawal visit.

LVEF assessment will be performed through echocardiography or MUGA scan at inclusion and at the withdrawal visit.

Results of LVEF assessment and ECG performed in the frame of previous CL2-95014-002 study withdrawal visit can be used to assess patient's inclusion in order to avoid unnecessary exam

Post-withdrawal follow-up: After the withdrawal visit, a contact or telephone call will be done approximately 30 days after the last S95014 infusion, except in case of consent withdrawal. The following information will be collected:

- follow-up adverse events
- the first new anticancer treatment after withdrawal and its starting date.

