1.2.1. Study plan

Written informed consent and assent (when appropriate) will be obtained from each patient and/or his/her parent(s)/legal representative during the inclusion visit, corresponding to the withdrawal visit of the initial CL2-95014-002 study.

S95014 lyophilizate will be administered IV every two weeks during the consolidation phase at the dose of 1000, 2000 or 2500 U/m², as per investigator's judgment. Patients will be administered 9 infusions of S95014 lyophilizate, at weeks 7, 9, 11, 15, 17, 19, 23, 25 and 27. Patients will receive other backbone chemotherapy agents as per ALL-MB 2015 protocol (see study protocol Appendix 1).

The study duration will be approximately 7 months, including the treatment period consisting of the consolidation phase and the follow-up period. After completing the consolidation phase, patient will be discontinued from the study and will be treated as per investigator's judgment.

The study will be divided into the following periods for each participant:

- **Inclusion visit:** to obtain informed consent and check the inclusion/non-inclusion criteria. The inclusion visit of CL2-95014-003 study will correspond to the withdrawal visit of the initial CL2-95014-002 study.
- **Treatment period:** As per ALL-MB 2015 protocol, treatment period will start at Day 1 of the consolidation phase. Patients will be on treatment until the end of the consolidation

[figure not shown]

phase, unless they meet a discontinuation criterion as described in the Clinical Study Protocol.

- **Withdrawal visit:** no later than 30 days after the last dose of S95014 during the consolidation phase. Patient will continue receiving backbone chemotherapeutic regimen as per ALL-MB 2015 protocol, according to physician's judgment.
- **Follow-up visit:** should be made after Withdrawal visit, a contact or telephone call will be done not earlier than 30 days after the last S95014 infusion, except in case of consent withdrawal. Follow-up of adverse events and the patient's survival will be recorded.

The study plan is shown in Figure (1.2.1) 1.

Figure (1.2.1) 1 - Study plan

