3.5.1. Adverse Events

A treatment-emergent adverse event (TEAE) is defined as any untoward medical occurrence in a subject who received IMP (S95014), which occurs within the period from the Inclusion visit, until 30 days after the last S95014 infusion, or the date of withdrawal, whichever is earlier. TEAE will be assessed according to the National Cancer Institute (NCI) Common Terminology Criteria Adverse Events (CTCAE) v5.0. Clinically significant laboratory abnormalities will be classified into Common Terminology Criteria (CTC) grade according to CTCAE v5.0 and will be reported as adverse events if they are associated with signs and symptoms or, clinically significant in the investigator's opinion except if related to the disease, if they require curative therapies, if they induce change of study treatment administration. All analyses described below will be based on TEAEs, if not otherwise specified.

Adverse events will be summarized in hierarchical tables, presenting the number and percentage of subjects having at least one AE, and having at least one AE in each primary system organ class and for each preferred term using MedDRA coding. AEs will be sorted by descending frequency, and alphabetically where frequency is tied. Such summaries will be produced for all AEs, serious adverse events (SAEs), grades 3 or 4 AEs, AEs leading to study treatment discontinuation, and AEs leading to dose-adjustment or interruption of any of the drugs of the treatment. All of these summaries will be by system organ class, preferred term, starting dose level if applicable and, in some case, worst grade. Most of the summaries will be produced twice, once for all events regardless of study treatment relationship, and once for events suspected to be study treatment related. All deaths will be listed and summarized. All AEs will be listed, and any other information collected (e.g., start/end dates and duration of adverse event, severity or relatedness to study medication) will be listed as appropriate.

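### SAP 3.5.1 can close the TEAE window at an undefined date of withdrawal, so SAEs the protocol collects to day 30 may be missing from the AE tables

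*SAP*

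**What the plan says.** SAP 3.5.1 opens the TEAE window at the Inclusion visit and runs it "until 30 days after the last S95014 infusion, or the date of withdrawal, whichever is earlier". Unless otherwise specified, the AE analyses that follow use TEAEs only. The SAE, grade 3-4 and treatment-related summaries carry no exception. The same section also promises a listing and summary of all deaths and a listing of all AEs, without saying whether these are limited to TEAEs.

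The scheduled withdrawal visit falls "up to 30 days after the last dose of S95014 during the consolidation phase" in Protocol 4.1.1 and "no later than 30 days after the last dose of S95014 during the consolidation phase" in SAP 1.2.1. Neither gives an earliest day. A follow-up contact comes after it: Protocol 8.2 places it "approximately 30 days after the last S95014 infusion, except in case of consent withdrawal", and SAP 1.2.1 says "a contact or telephone call will be done not earlier than 30 days after the last S95014 infusion".

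Protocol 8.9.1 sets two collection periods after dosing starts. All events are reported up to the withdrawal visit. Events requiring immediate notification (ERIN) are reported up to 30 calendar days after the last dose, whatever their cause. Protocol 8.7 puts every SAE in the ERIN group.

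**The concern.** The closing date of the window is not defined, and the rule takes the earlier of two dates, so the meaning of the second date decides which events are counted. The documents use withdrawal in three senses: the scheduled visit that every patient attends, premature withdrawal from the study (Protocol 5.6), and withdrawal of consent. Under the first two senses, tabulation can stop before the protocol stops collecting SAEs.

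This matters because safety is the secondary objective and the only outcome with a planned analysis; Protocol section 7 lists efficacy as not applicable. An SAE that is in a listing but not in the SAE table lowers the reported frequency. Protocol 10.2.1.1 plans the same summaries with no TEAE restriction. The SAP adds the restriction, yet its section 6 reports no change from the planned analysis.

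**Working it through.** No sample-size or power figure is involved. The check compares the tabulation and collection windows, in days after the last infusion.

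**Inputs**

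- End of TEAE window: the earlier of day 30 and the date of withdrawal (SAP 3.5.1).
- Withdrawal visit: day w, with w ≤ 30 (Protocol 4.1.1, SAP 1.2.1). No value of w is given.
- End of SAE collection: day 30 (Protocol 8.9.1 with 8.7).
- End of required collection of non-serious AEs: day w (Protocol 8.9.1).
- Infusions "at week 7, 9, 11, 15, 17, 19, 23, 25 and 27" (Protocol 6.1.1).

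**Reading 1: the withdrawal visit.** Usage elsewhere gives some support. Protocol 6.3 records other treatments "during the period from the day of informed consent to the withdrawal day", and Protocol 8.1 says abnormalities "from the patient ICF signature until the withdrawal visit must be reported". The window then ends at min(30, w) = w, and the collected SAE time left out is 30 - w days. For scale, a completer has (27 - 7) × 7 = 140 days from first to last infusion, plus 30, giving 170 days. Every w below is an assumption.

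| Assumed w | SAE days left out (30 - w) | Share of 170 days |
|---|---|---|
| 7 | 23 | 13.5% |
| 14 | 16 | 9.4% |
| 21 | 9 | 5.3% |
| 28 | 2 | 1.2% |
| 30 | 0 | 0% |

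The shares are slightly too high, because the SAP window opens at inclusion, before the first infusion. For non-serious AEs, required collection and the window both end on day w, so the systematic gap is w - w = 0 days.

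**Reading 2: premature withdrawal.** Protocol 5.6.1 equates stopping the IMP early with leaving the study early, and adverse events are among the listed reasons. If such a patient withdraws p days after the last infusion, the SAE time left out is max(0, 30 - p): 30 days at p = 0, and none from p = 30 onward. The event that caused the stop begins before that date and is still counted; later SAEs are not. Completers are unaffected. The documents give neither the number of early stoppers nor p.

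**Reading 3: consent withdrawal.** The follow-up contact is not made in that case (Protocol 8.2, SAP 1.2.1), so there is little or no collected data to exclude.

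**With the withdrawal limb removed.** The window and SAE collection both end on day 30, so the gap is 30 - 30 = 0 days for every w and p. What remains is a stretch of 30 - w days in which non-serious events are tabulated if recorded, but their reporting is not required.

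**The case against.** The strongest reply is that the visit reading is not clearly the intended one. Under it the 30-day limb does nothing for any patient whose visit is on schedule, and SAP 3.5.1 does not use the term for the visit that SAP 1.2.1 has already set up. The other two readings give both limbs work, and their effect is smaller. This stands: a reader might infer that the visit is the natural meaning and that every patient's late SAEs are dropped, but the documents do not establish that.

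It can also be argued that closing at the visit is defensible, because it keeps the tables to a period in which serious and non-serious events are both collected. That is a fair reason for a cut-off in the all-AE table. It does not justify leaving collected SAEs out of the SAE table.

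The study is descriptive, with no comparator, hypothesis test or interim analysis, and the table templates are in a separate document that may define the date. Both points limit the consequence. It cannot be shown that programmers would in fact apply different cut-offs, only that the SAP text would allow it.

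Two stronger inferences fail. SAEs are not lost from the study: they are reported, and may appear in the AE listing and the deaths summary. Nor are non-serious AEs systematically dropped under the visit reading, because their required collection ends at the same visit.

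**Conclusion.** The point holds as a conditional one. SAP 3.5.1 contains an operative cut-off whose date is undefined. On two of the three available readings it leaves collected SAEs out of the SAE, grade 3-4 and related-event tables. That is more than a missing definition, because the rule can shorten tabulation below what the protocol collects.

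The size is 30 - w days per patient on the visit reading, confined to early stoppers on the premature-withdrawal reading, and negligible on the consent reading. The figures for w are illustrations: the documents support only w ≤ 30, and w = 30 gives no loss. The number of affected events cannot be estimated. The consequence is possible under-counting in the tables, with the data retained. Severity is minor to should-fix.

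**What to change.** In SAP 3.5.1, delete the date-of-withdrawal alternative. End the TEAE window at last S95014 infusion + 30 days for every treated patient, cut earlier only by consent withdrawal or, for patients lost to follow-up, by the last contact date. Apply this one window to all AE tables, so that no patient can count in the SAE table but not in the all-AE table.

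Add a footnote to the AE tables: Protocol 8.9.1 requires non-serious AEs only up to the withdrawal visit, so between that visit and day 30 only ERIN are required, plus whatever is recorded at the follow-up contact. The second part is needed because the Protocol 4.1.2 schedule marks adverse events at the follow-up visit.

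The cost is SAP wording and one footnote, with no new visits or data. It can be done before the SAP is finalised, which Protocol 10.5 requires before database lock. The drawback is less complete collection of non-serious events in the last days of the window; the footnote discloses this but does not remove it.

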2.2.2. PEGylated asparaginase development and status

Oncaspar® (pegaspargase; S95014) is a variation of the enzyme L-asparaginase modified by covalently bonding units of monomethoxy polyethylene glycol (PEG) to the enzyme, forming the active pharmaceutical ingredient PEG-L-asparaginase.

In the United States (US), S95014 received approval in 1994 for second-line use in acute lymphoblastic leukaemia (ALL) following the development of hypersensitivity to native L-asparaginase. In 2006, the US authorization of S95014 was expanded to include first-line treatment of ALL.

Pegaspargase is now very well established in clinical practice in the first-line treatment of ALL and is licensed in many countries ([Heo YA et al, 2019](#)). It has been determined by the World Health Organization (WHO) an essential medication needed to meet the needs of a health system and is included in the List of Essential Medicines (WHO 2019).

The safety profile of pegaspargase has also been well characterized over these last 25 years of consistent use in ALL treatment protocols. The most common (>5%) grade ≥ 3 AEs included hepatotoxicity (elevated transaminases, increased bilirubin and hypoalbuminemia), febrile neutropenia, hypertriglyceridemia, hyperglycemia, pancreatitis, coagulopathy, embolic and thrombotic events, and hypersensitivity. For further details, please refer to the last version of the [Investigator's Brochure](#).

So far, S95014 is not approved yet in Russia and the product is only available through a non-governmental organization (NGO) special request. Thus, patients treated in ALL-MB 2015 protocol are administered S95014 during the induction phase (one dose) and native L-asparaginase during the consolidation phase. Once approved, S95014 is expected to play an important role in Russia as a first-line treatment for ALL.

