5.6. Participant withdrawal

5.6.1. Withdrawal criteria

Premature discontinuation of IMP corresponds to participant prematurely discontinuation of the study.

Information to be collected during the last visit of these participants is given in [section 5.6.2](#). These follow-up modalities are used to ensure safety evaluation of all participants who received the IMP.

The reasons for premature discontinuation of IMP are:

- **Adverse events** according to the judgement of the investigator or according to the criteria defined in [section 8.10](#)
- **Pregnancy** ([section 8.9.2.3](#))
- **Major deviation to protocol** if it interferes with the study evaluations and/or if it jeopardises participant's safety
- **Progressive disease** documented with appropriate method of evaluation according to disease characteristics
- **Non-medical reason** (e.g. consent withdrawal, participant's removal)
- **Other, physician decision**

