8.10. Management of toxicities

An AE for which a causal relationship to S95014 is evidently ruled out will not be considered toxicity. For patients who do not tolerate the protocol-specified dosing schedule, dose interruptions and/or reductions are either recommended or mandated during the consolidation phase.

The results of laboratory tests should be available before the S95014 administration in order to comply with management of toxicities if applicable.

For each patient, once a dose reduction has occurred, the dose may not be re-escalated during the treatment period unless there is documented agreement with the Sponsor.

Table (8.10) 1 - Criteria for S95014 interruption or discontinuation

Toxicity	Action to be taken
Hypersensitivity	
Grade 1 hypersensitivity	Symptomatic treatment Infusion rate should be reduced by 50%
Grade 2 hypersensitivity	S95014 infusion interruption Symptomatic treatment Upon recovery, infusion can be resumed with an infusion rate reduced by 50%
Grade 3-4 hypersensitivity	S95014 discontinuation Symptomatic treatment Switch to Erwinase should be considered as per investigator's judgment
Pancreatitis	
Grade 2 pancreatitis	S95014 interruption until recovery
Clinical pancreatitis (Grade 3-4)	S95014 discontinuation*
Hepatotoxicity	
Grade 3 ALT and/or AST increase	S95014 interruption, can be resumed if resolved \leq Grade 2
Grade 4 ALT and/or AST increase	If not recovered within 2 weeks: S95014 discontinuation If resolved (\leq Grade 2) within 2 weeks: S95014 can be resumed
Grade 3 total bilirubin increase	S95014 interruption, can be resumed if resolved \leq Grade 2
Grade 4 total bilirubin increase	S95014 discontinuation*
Haemorrhage	
\geq Grade 2 haemorrhage	S95014 interruption until resolves to Grade 1
Grade 4 haemorrhage	S95014 discontinuation
Thrombosis	
Grade 3 thrombotic event	S95014 interruption until recovery
Grade 4 or serious thrombotic event	S95014 discontinuation

**in case of high-risk of relapse, S95014 might be reintroduced at a lower dose as per investigator's judgment*

Prophylactic treatment for hypersensitivity should be administered as per local practice.

For further details about the management of S95014 toxicities, please refer to ALL-MB2015 protocol ([Appendix 1](#)) and [Investigator's Brochure](#).

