9.2. Measurement of plasma asparaginase activity

Plasma Asparaginase Activity will be assessed before next S95014 infusion during the consolidation phase, as per local practice. PAA will be determined using a coupled enzymatic activity assay validated according to current regulatory guidelines. If asparaginase activity values fail to reach target levels, a switch to a different asparaginase preparation could be considered.

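### The SAP's treatment-emergent window ends on an undefined withdrawal date and has no flag for a switch to another asparaginase, so events after a switch may be tabulated as S95014 events

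*SAP*

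**What the plan says.** **The window.** SAP 3.5.1 opens the TEAE window at the inclusion visit and runs it "until 30 days after the last S95014 infusion, or the date of withdrawal, whichever is earlier". Unless otherwise stated, all AE tables rest on TEAEs. The SAP does not say what the date of withdrawal is, and nothing in the section refers to the start of another asparaginase.

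**The switch.** The Protocol foresees one in two places. After grade 3-4 hypersensitivity, Table (8.10) 1 stops S95014 and adds: "Switch to Erwinase should be considered as per investigator's judgment". When asparaginase activity is below target, section 9.2 says that "a switch to a different asparaginase preparation could be considered".

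**What follows from stopping.** Protocol 5.6.1 states: "Premature discontinuation of IMP corresponds to participant prematurely discontinuation of the study". The withdrawal visit has no fixed day. Protocol 4.1.1 places it "up to 30 days after the last dose of S95014 during the consolidation phase", and SAP 1.2.1 "no later than 30 days after the last dose of S95014 during the consolidation phase".

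**What is collected.** Protocol 8.9.1 collects all events to the withdrawal visit. It collects events requiring immediate notification, which include SAEs, to day 30 after the last dose whatever their supposed cause. Protocol 6.3 records the name and the start and end dates of any drug other than S95014 and backbone therapy, from consent to the withdrawal day. At the later contact, Protocol 8.2 asks for "the first new anticancer treatment after withdrawal and its starting date".

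**The concern.** The safety profile of lyophilized S95014 is the only objective that is analysed. A child who moves to another asparaginase can still be inside the S95014 window when a reaction to the new product occurs. That event would then stand in an S95014 table with nothing to mark it. The children concerned are not a random subset: they have reacted badly or had low activity, and they are the ones whose later events a reader will look at most closely.

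The tables restricted to related events are a weak screen. Protocol 8.8 treats an event as related whenever a relationship to the IMP cannot be excluded, and SAP 3.2 counts a missing causality as related. An asparaginase-type reaction within 30 days of a pegylated asparaginase will often meet that test.

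The undefined date also matters in the other direction. If it falls early, events that the Protocol deliberately collects are left out of the tables.

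**Working it through.** The plan gives no figure on this point to reproduce. The study is descriptive, and neither document states a switch rate. The check is therefore of the window itself.

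**Inputs**
- Infusion weeks 7, 9, 11, 15, 17, 19, 23, 25, 27 (Protocol 4.1.1, SAP 1.2.1). The gaps in days are 14, 14, 28, 14, 14, 28, 14, 14: six of 14 days, and two of 28 days (weeks 11-15 and 19-23).
- Window cap: day 30 after the last S95014 infusion (SAP 3.5.1).
- Withdrawal visit: any day up to day 30 (Protocol 4.1.1, SAP 1.2.1).
- Planned number: about 88 (Protocol synopsis).

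**Formula.** Let S be the day of the first dose of the replacement and W the day of withdrawal, both counted from the last S95014 infusion. Post-switch days inside the window = max(0, min(30, W) − S).

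| Switch day S | Visit on day 30 | Visit on day 14 | W = discontinuation, on or before S |
|---|---|---|---|
| 2 | 30 − 2 = 28 (93%) | 14 − 2 = 12 | 0 |
| 7 | 30 − 7 = 23 (77%) | 14 − 7 = 7 | 0 |
| 14 (next dose, 14-day gap) | 30 − 14 = 16 (53%) | 0 | 0 |
| 28 (next dose, 28-day gap) | 30 − 28 = 2 (7%) | 0 | 0 |

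The percentages are shares of the 30 days after the last dose, not event rates.

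**The other side of the definition.** If W is the discontinuation date, every event between that date and day 30 lies outside the window, including SAEs that Protocol 8.9.1 requires to day 30. An early visit has a milder form of the same effect: with a visit on day 14, the last 30 − 14 = 16 days of SAE collection are outside the TEAE tables.

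**Size.** One child is 1/88 = 1.1 percentage points. The tables count subjects with at least one event, so a repeat of a preferred term already counted for that child adds nothing. Only a new preferred term or a higher worst grade changes a cell. Let s be the share of children who switch, and q the share of switchers whose first event of a given type falls after the switch and inside the window. The added incidence is then s × q. Neither value is in the documents. Assuming s = 5% to 20% and q = 10% to 30%:
- low end: 0.05 × 0.10 = 0.5 points, or 88 × 0.005 = 0.4 children;
- high end: 0.20 × 0.30 = 6 points, or 88 × 0.06 = 5.3 children.

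Tables by starting dose have smaller denominators, so one child weighs more there. The documents do not give the split.

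**The case against.** The strongest reply is that the rule already closes the window. Stopping the IMP ends study participation under Protocol 5.6.1, and SAP 3.5.1 takes the earlier of two dates. If withdrawal means the discontinuation date, no post-switch day is counted. This stands as one of two possible readings. It rules out the inference that the window always runs on after a switch, but it does not settle which reading the SAP intends, and it has the cost shown above for late SAEs.

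A reader might also infer that a replacement begun before the withdrawal visit goes unrecorded, because the item in Protocol 8.2 concerns treatment after withdrawal. The documents do not support this: Protocol 6.3 already takes the name and start date of such a drug. Nor do they establish that native L-asparaginase is exempt as backbone. Protocol 2.2.2 describes "native L-asparaginase during the consolidation phase" as the practice for patients on ALL-MB 2015, but the consolidation backbone list in Protocol 6.1.2 contains no asparaginase. With Appendix 1 not available here, this needs only a confirmation.

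It is also tempting to read 53% or 93% as the inflation of S95014 event rates. They are maximum shares of days under a day-30 visit. The one named switch follows severe hypersensitivity, and a repeat under a preferred term already recorded for that child leaves its incidence unchanged. The documents also give no toxicity profile for Erwinase, so how far the toxicities of the two products overlap is partly an assumption.

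Finally, an event after a switch may be a late effect of S95014 itself, since the pegylated forms were developed partly because the native enzyme is cleared quickly (Protocol 2.1). This stands, and it argues against removing such events from the main tables.

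**Conclusion.** The gap is real but conditional. SAP 3.5.1 ends the window on an undefined date, and each reading has a defect. Under the visit-date reading, unmarked post-switch events enter the S95014 tables, with between 0 and 28 of 30 days exposed in the cases worked above. Under the discontinuation-date reading there is no contamination, but SAEs collected to day 30 are lost from the TEAE tables.

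The effect should touch only a few children: 0.4 to 5.3 for any one type of event under the assumed ranges, at 1.1 points each. It does not call the overall safety description into question. The documents do not support the stronger claim that the replacement product's toxicity is in every case counted against S95014. This is a cheap improvement to a descriptive analysis, and it implies nothing about whether or when a switch should be made.

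**What to change.** - In SAP 3.5.1, define the date of withdrawal consistently with the collection periods in Protocol 8.9.1, so that SAEs collected to day 30 have a stated place in the tables. Use the same definition for the recording items in Protocol 6.3 and 8.2, so that the two meet without a gap.
- Keep the window and the main tables as they are.
- Derive a flag for TEAEs with onset on or after the first dose of another asparaginase, from the start dates already collected under Protocol 6.3 and 8.2. Show the AE tables with and without flagged events.
- Confirm in the eCRF instructions that any replacement asparaginase, including native L-asparaginase, is recorded under Protocol 6.3 and not treated as exempt backbone.

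The cost is one definition, one derived flag, one recording clarification and one extra set of tables. No new eCRF field should be needed, treatment is unchanged, and no event is dropped from the main tables.
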